## 22 Appendix D: Arm 3: Fostamatinib

### 22.1 Description of active therapy

Fostamatinib is an oral spleen tyrosine kinase inhibitor FDA approved for the treatment of adult patients with chronic immune thrombocytopenia (ITP) who have had insufficient response to previous treatment. Fostamatinib is a prodrug with an active metabolite, R406. R406 is protein bound and has a half-life of 15 hours, with 80% of excretion occurring in feces and 20% excreted in urine.

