**Figure 2. Spleen tyrosine kinase inhibition in COVID-19 ([name], Generated using Biorender)**

### 22.3 Fostamatinib dose, duration, and route of administration

We will use a study dose of 150mg orally twice daily for 14 days (28 doses). This regimen was studied in the recently completed phase 2 trial in patients hospitalized with COVID-19. The dose may be modified to 100mg according to pre-defined criteria in section 22.7 (Dose Modification Considerations and Medication Interactions). Study medication will be continued as an outpatient if the patient is discharged prior to completing 28 doses. If necessary, in patients unable to swallow, tablets can be crushed until granular with an approximate particle size <2 mm, added to approximately 10 mL of water, and stirred to mix before administration through an enteral tube.

While many patients on BiPAP can safely receive oral medications, it may be potentially unsafe to administer oral medications to patients at certain times while they are receiving BiPAP therapy due to risk of hypoxemia if the mask is removed and/or risk of aspiration if an oral medication is administered and BiPAP is immediately re-initiated. Determining whether an oral medication should be given to a patient receiving BiPAP therapy is a bedside clinical decision.

The goal is to administer two doses of study medication each calendar day and approximately 12 hours apart from one another. If the time between study medication doses needs to be reduced, the recommendation is to administer two doses at least 4 hours apart from one another. If a dose of study medication is entirely skipped, a missed dose should be noted in the electronic data capture

system (REDCap). Skipped doses are not “made up” by extending the dosing period; patients should only receive study drug for a maximum of 14 days, starting with randomization.

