## **22.7 Dose Modification Considerations and Medication Interactions**

**Dose Modifications:** The following dose modifications will be utilized in patients randomized to the fostamatinib arm (active or placebo). Those patients who have doses held will only complete 14 days (up to 28 doses) of study treatment. Dosing will not extend beyond day 14. Blood pressure will be monitored daily in the hospital while on study drug up until the time of discharge.

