3.3 Safety Outcomes

Safety outcomes include the following events, assessed daily during hospitalization or intermittently following hospital discharge. For each event, we will analyze two composite binary outcomes: 1) the occurrence of one or more such events by the end of study day 7 and 2) the occurrence of one or more such events by the end of study day 28.

Description	Type	Analysis Method
Hypotension	Binary	LogR
Allergic reaction, rash, or angioedema	Binary	LogR
Incident renal replacement therapy	Binary	LogR
Other PSESE	Binary	LogR

LogR – Logistic Regression

Hypotension is defined by low arterial blood pressure leading to either [1] initiation or increase in vasopressor therapy, [2] administration of a fluid bolus of 500 ml or more, or [3] modification of the dose or discontinuation of the study drug.

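### No comparative safety outcome matches fostamatinib's 14-day dosing period: SAP 3.3 stops at day 7 or runs to day 28, so a day-14 outcome would be a cheap addition

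*SAP*

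**What the plan says.** SAP 3.3 lists four safety outcomes (hypotension; allergic reaction, rash or angioedema; incident renal replacement therapy; other PSESE) and applies the same rule to all arms: "For each event, we will analyze two composite binary outcomes". The first is one or more events "by the end of study day 7" and the second is "the occurrence of one or more such events by the end of study day 28". SAP 7.1.2 analyses each by adjusted logistic regression, giving an odds ratio and a difference in proportions with 95% credible intervals. SAP 5 excludes hypothesis tests for safety outcomes.

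Protocol 22.3 sets the fostamatinib course: "We will use a study dose of 150mg orally twice daily for 14 days (28 doses". It adds: "Study medication will be continued as an outpatient if the patient is discharged prior to completing 28 doses". Protocol 22.7 closes the period: "Dosing will not extend beyond day 14". Protocol 22.1 says the active metabolite R406 "has a half-life of 15 hours", and Protocol 13 expects drug effects during treatment or soon after it.

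SAP 7.2 leaves agent-specific safety endpoints to the agent's appendix. Appendix D supplies monitoring rules, a list of expected events and one adverse event of special interest (22.7 and 22.8), but no further comparative window.

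**The concern.** The safety comparison is most informative when its window follows the period at risk from the drug. For this arm neither window does. Day 7 closes with about half of the course still to come, some of it taken at home. Day 28 counts roughly two weeks in which, on the protocol's own reasoning, little drug effect is expected but COVID-19 complications can still occur in both groups.

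This touches the drug's known risks. Hypertension, raised transaminases and neutropenia are named in Protocol 22.5 and are PSESEs under Protocol 13.2, so they enter the comparison through the other-PSESE outcome. The same list holds background events such as ARDS, ventilation and kidney injury. At stake is how sharply the final report can describe on-treatment risk.

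**Working it through.** **Coverage.** 2 doses a day × 14 days = 28 doses, which agrees with Protocol 22.3. Day 7 covers 7 of 14 dosing days (50%), or 8 of 14 (57%) if dosing runs from day 0 to day 13. Day 28 adds 28 − 14 = 14 days after dosing. Five half-lives of R406 are 5 × 15 = 75 hours, about 3.1 days.

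**Size: inputs.** From the documents: about 300 active and 300 placebo participants (SAP 6.6), and dosing to day 14. Assumed, because the documents give no safety rates: total background hazard of 0.14 over 28 days (0.5% a day if constant), hazard doubled through day 14, no excess afterwards. The value z > 1.96 serves only as a signal-to-noise yardstick.

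**Formulas.** Background cumulative hazard to day t: H0 = 0.14 × t/28 if constant, or 0.14 × (1 − 0.5^(t/k)) / (1 − 0.5^(28/k)) if it decays with half-time k days. On drug, H1 = H0 plus the background hazard accrued up to day 14 (or up to t, if earlier). Risk p = 1 − exp(−H). z = (p1 − p0) / √[p0(1 − p0)/300 + p1(1 − p1)/300]. Chance = 1 − Φ(1.96 − z). Odds ratio = (exp(H1) − 1) / (exp(H0) − 1).

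**Constant background hazard.**

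| Window | H0 | H1 | p0 | p1 | SE | z | Chance | Odds ratio |
|---|---|---|---|---|---|---|---|---|
| Day 7 | 0.035 | 0.070 | 0.0344 | 0.0676 | 0.0179 | 1.85 | 46% | 2.04 |
| Day 14 | 0.070 | 0.140 | 0.0676 | 0.1306 | 0.0243 | 2.60 | 74% | 2.07 |
| Day 28 | 0.140 | 0.210 | 0.1306 | 0.1894 | 0.0298 | 1.97 | 50% | 1.56 |

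From day 14 to day 28 the risk difference barely moves (0.1306 − 0.0676 = 6.3 points; 0.1894 − 0.1306 = 5.9 points), while its standard error grows from 2.4 to 3.0 points. So the odds ratio is diluted and the risk difference mainly loses precision.

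**Changing the level.** At 0.2% a day z is 1.18, 1.66 and 1.28 for days 7, 14 and 28; at 1% a day it is 2.60, 3.60 and 2.67. The ordering holds.

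**Changing the shape, same total hazard of 0.14.**

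| Background | Chance: day 7 | Day 14 | Day 28 | Odds ratio: day 14 | Day 28 |
|---|---|---|---|---|---|
| Constant | 46% | 74% | 50% | 2.07 | 1.56 |
| 10-day half-time | 69% | 87% | 78% | 2.11 | 1.82 |
| 5-day half-time | 83% | 92% | 90% | 2.13 | 2.00 |
| 3-day half-time | 90% | 94% | 94% | 2.14 | 2.10 |

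The gain of day 14 over day 28 falls from about 24 points (74 − 50) to 9, 2 and almost none.

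**Changing when the excess occurs.** With constant background and the hazard doubled on days 1 to 7 only, H1 is 0.070, 0.105 and 0.175 at days 7, 14 and 28. The chances are 46%, 29% and 18%. Day 7 is then the best window.

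**The case against.** The strongest reply is that common windows suit a platform with pooled placebo, and that on-treatment safety is well covered elsewhere. Table 2 of the protocol collects adverse events and PSESEs at day 14, the DSMB sees PSESEs unblinded by arm (Protocol 13.2), safety monitoring is continuous (SAP 7.2), and Protocol 22.7 adds daily inpatient blood counts, liver tests and blood pressure. This stands as a limit on the stakes. These are collection and surveillance provisions, however, and none supplies a prespecified comparison over the dosing period. A common analysis approach also does not bar an arm-specific addition, since Protocol 8.1 provides for arm-specific SAP amendments.

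Four stronger readings are tempting, and the documents do not support them.

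- A reader might infer that late on-drug toxicity goes uncounted. It does not: the day-28 outcome includes every event from days 8 to 14.
- A reader might infer that a safety test is underpowered. SAP 5 plans none, and no decision rule in SAP 3.3 uses either window.
- A reader might take the 24-point gap as the expected loss. It needs a constant background hazard. The documents give no event timing, but acute enrolment (within 72 hours of hypoxemia, Protocol 6.2) and the quoted median stay of 10 to 13 days (Protocol 3.1) make declining risk plausible, and the gap then shrinks.
- A reader might conclude that day 14 should replace day 7. If toxicity is confined to week 1, that swap would lose signal (46% against 29%).

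**Conclusion.** The mismatch is real and follows from the documents alone: neither comparative safety window corresponds to the 14-day fostamatinib exposure. Its consequence is modest: a less targeted and less precise estimate of on-treatment risk, with a day-28 odds ratio that may sit closer to 1. How much closer depends on event timing that the documents do not give. Under the stated assumptions the day-28 odds ratio ranges from 1.56 (constant background) to 2.10 (3-day half-time), against 2.07 to 2.14 at day 14. Where the excess lasts through the dosing period, day 14 did at least as well as either planned window in every shape tried. Where the excess is confined to the first week, it did not. This is a worthwhile refinement, not the correction of an error.

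**What to change.** In SAP 3.3, for the fostamatinib arm and its eligible placebo comparators, add a third binary outcome per safety event: one or more events by the end of study day 14. Keep days 7 and 28. State whether the window includes a short post-dose lag and how its length was chosen in light of R406's 15-hour half-life.

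The cost is one more set of logistic models and one more descriptive comparison per safety event, plus approval of an SAP amendment under SAP 1.2. No new data are needed: inpatients are assessed daily, and discharged participants are already contacted at day 14 (Protocol Table 1). Dosing and clinical management are unaffected.

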3.4 Exploratory Outcomes

Exploratory outcomes will include (at least) the following:

Description	Type	Analysis Method
Change in troponin during hospitalization	Quantitative	LinR
Change in NT-proBNP	Quantitative	LinR
Change in RAAS mechanistic biomarkers: 1. AngII 2. Ang(1-7) 3. Plasma renin activity 4. Aldosterone 5. ACE 6. ACE2	Quantitative	LinR
Change in serum creatinine	Quantitative	LinR
Change in eGFR	Quantitative	LinR
Acute kidney injury (KDIGO criteria)	Ordinal	POLR

LinR – Linear Regression; POLR – Proportional Odds Logistic Regression

Exploratory outcomes may be collected at just a subset of sites.

4 ANALYSIS DATASETS

For each study arm, the following analysis datasets will be produced using records for participants that were assigned to the active drug group and placebo participants that were *eligible* for the active drug group at the time of randomization:

Modified intention-to-treat dataset: The mITT analysis dataset will include all randomized participants grouped by study arm and active/placebo assignment at randomization, regardless of subsequent compliance or protocol violations, with the following exceptions: 1. Participants who have not received the study drug assigned at randomization will be excluded. 2. Participants who were randomized and later found to be ineligible based on assessments initiated prior to randomization will be excluded. All statistical analyses will be implemented using mITT dataset unless otherwise explicitly specified in this statistical analysis plan.

Intention-to-treat dataset: The intention-to-treat (ITT) analysis dataset will consist of all randomized participants grouped by study arm and active/placebo assignment at randomization regardless of subsequent compliance or protocol violations.

Safety dataset: The safety analysis dataset will consist of all participants grouped by the drug(s) received.

5 EFFICACY TESTING & FAMILYWISE TYPE-I ERROR CONTROL

Efficacy regarding the primary outcome and each key secondary outcome will be tested using a one-sided method that ensures no more than a 2.5% chance of a type-I error. The fixed-sequence method will be used to control the familywise type-I error probability at 2.5% for the family of primary and key secondary outcomes.¹ Specifically, a conclusion of efficacy regarding the primary outcome will be required prior to testing the first designated key secondary outcome. Each subsequent key secondary outcome, in the designated order, will take place only if the preceding key secondary outcome demonstrates efficacy. This approach provides strong control of the familywise type-I error probability at 2.5% for the family of primary and key secondary outcomes. No other statistical hypothesis tests will be made regarding other secondary, safety, or exploratory outcomes. P-values associated with certain null hypothesis tests may be provided for descriptive purposes, or to fulfill special requests, e.g., for DSMB safety assessments.

6 ANALYSIS OF THE PRIMARY OUTCOME

The effect of the active drug versus placebo will be quantified using an odds ratio – the primary estimand – which quantifies the treatment effect on the odds of greater oxygen-free days at day 28. Based on the behavior of similar outcomes in prior trials,²⁻⁶ we anticipate the distribution of the primary outcome to be irregular, with peaks around -1 to 0 and between 22 and 28 days. Thus, we will use a flexible semi-parametric approach for the primary outcome analysis. Estimation and inferences about the odds ratio will be made using Bayesian proportional odds (PO) logistic regression methods, adjusting for the active drug vs placebo indicator variable, age group (18-30, 31-65, >65 years), sex at birth, and WHO COVID ordinal outcome score at baseline (4, 5, and 6-7).⁷ Evidence for efficacy will be quantified using the posterior probability that the active drug versus placebo odds ratio is greater than one (i.e., treatment is associated with greater oxygen free days at day 28). This is denoted the “efficacy probability” or $P(\text{OR} > 1 | \text{Data})$, where OR represents the odds ratio, and Data represents the mITT analysis dataset. The “inferiority/harm probability” is defined as $P(\text{OR} \leq 1 | \text{Data})$. The primary analysis will be implemented separately for each study arm, where the placebo comparator group will consist of placebo participants that were eligible for the corresponding study arm at randomization, regardless of the study arm assigned. The primary and supplementary estimates will be presented with 95% credible intervals.

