### **6.7 Randomization and blinding**

Randomization assignments are performed for patients at enrollment. Randomization will be implemented using a permuted block method and stratified by site and eligibility group. The eligibility group for each participant is the set of study arms for which the participant is eligible. Participants are not eligible for arms that have not begun or have ceased enrollment. Stratification by site ensures balance across the active and pooled placebo groups at regular enrollment intervals at each site, thus mitigating the impact of site heterogeneity on assessments of treatment effect. Eligible participants will be randomized through a central electronic system. On entry to the study and confirmation of eligibility to at least one active drug arm, the participant will be randomized m:1 to either the active (will receive one of the study drugs) or placebo (will not receive one of the study drugs) condition. Here, m is the number of open study arms for which the patient is eligible. If the patient is eligible for only one agent, or only one study arm is open, then allocation is 1:1. For two agents, it is 2:1, for three it is 3:1 and so on. Once participants are assigned as active or placebo, the participant will then be randomized with equal probability to receive one of the active drugs for which they are eligible, or a corresponding placebo (matched by route and frequency of administration). For the purposes of interim and final

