#### **8.6 Analysis of Primary Outcome**

##### **8.6.1 Primary Analysis**

The effect of each study agent versus matching placebo will be quantified using an odds ratio, which quantifies the treatment effect on the odds of greater values of the primary outcome. Estimation and inference about the primary estimand (and supplementary estimands) will be implemented using Bayesian PO logistic regression methods, adjusting for the active drug vs placebo indicator variable, age group (18-30, 31-65, >65 years), sex at birth, baseline WHO COVID

ordinal outcome score at baseline. Evidence for efficacy will be quantified using the posterior probability that the active agent versus placebo odds ratio is greater than one (i.e., treatment is associated with greater oxygen free days at day 28). This is denoted the “efficacy probability” or  $P(\text{OR} > 1|\text{Data})$ , where OR represents the odds ratio, and Data represents the available outcome data. The posterior probability for inferiority/harm is defined as  $P(\text{OR} \leq 1|\text{Data})$ . The primary analysis will be implemented separately for each study agent, where the matching placebo group will consist of concurrently randomized participants meeting the inclusion and exclusion criteria for that agent. The primary and supplementary estimands will be presented with 95% credible intervals. While we do not anticipate missing covariate data.

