2.2 Study Arms and Pooled Placebo

The ACTIV 4 Host Tissue platform consists of multiple study arms that represent distinct drug therapies. During the randomization process, each participant is assigned a study arm and either the active drug or a matching placebo. The statistical analyses described herein will be implemented separately for each study arm. However, placebo participants will be pooled across arms. For each study arm, the placebo comparator group will consist of all placebo participants that were *eligible* for that study arm at the time of randomization. A participant is considered eligible for a study arm if assignment to that arm was a possible outcome of randomization. Participants that decline to participate in any one or more study arms prior to

randomization will be treated as ineligible for those arms. The randomization process is designed to ensure balance in each active drug group versus the corresponding placebo comparator group.

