2.3 Randomization

Participants are randomized individually at enrollment using a central electronic system. The permuted block method, with stratification by study site and study arm eligibility is used to generate treatment assignments. An eligibility stratum is the collection of study arms for which a participant is eligible. Stratification by site ensures balance across the active and pooled placebo comparator groups at regular enrollment intervals at each site, thus mitigating the impact of site heterogeneity on assessments of treatment effect. Each block contains a multiple of $m(m+1)$ assignments, where m is the number of study arms in the corresponding eligibility stratum. Within each block there are an equal number of allocations across study arms and, for each study arm, there are m active and 1 placebo assignments. For example, in the TXA127 and TRV027 eligibility stratum, each block consists of the following allocations, or multiples thereof:

Study Arm	Placebo/Active
TXA127	Active
TXA127	Active
TXA127	Placebo
TRV027	Active
TRV027	Active
TRV027	Placebo

Thus, within each block, assignments are balanced across study arms, and the active assignments are balanced with the pooled placebo assignments. The block size multiple is either 1 or 2, selected uniformly at random for each block.

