Based on these data and effect size scenarios, a series of statistical simulations were implemented to examine the operating characteristics of the statistical study design described above, including the plan for randomization, statistical analysis method, interim analysis, and final assessments of efficacy using the odds ratio. In each simulation, participant age group, sex, and baseline WHO COVID severity score were randomly sampled with replacement from the values observed, and their effects on the primary outcome were simulated to match the estimated effects of age group, sex, and WHO score on the primary outcome among the first 100 participants. In order to assess the potential impact of attrition and loss-to-follow-up, partially observed oxygen free days were simulated to match the observed frequency of partially observed outcomes, which occurred in 12% of the first 100 participants. To encode attrition, a subset of the simulated study participants was selected at random, each with probability 0.12.

The primary outcome for each selected participant was encoded as partially observed by assuming that oxygen free days may have taken any value between -1 and a randomly sampled value ranging from the simulated oxygen free days to 28. For example, if the simulated oxygen free days is 10, then a value between 10 and 28 is sampled uniformly at random and this value is treated at the upper limit for the partially observed oxygen free days. This pattern of partially observed oxygen free days closely resembles the patterns observed among the first 100 participants. All simulation analyses, including those associated with interim and final assessment of efficacy and inferiority were implemented using the methods described above for the analysis of the primary outcome.

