Pr(Inferiority)	0.0.119	0.117
Pr(Inconclusive)	0.858	0.858
Average(N)	284.0	286.4

Prior to the start of enrollment, initial sample size assessments were based on pooled and blinded summaries of OFDs from the PassItOn (convalescent plasma) trial of patients hospitalized for COVID-19. The inclusion and exclusion criteria for PassItOn are similar to that for ACTIV 4 Host Tissue. In these initial assessments, the estimated MDE85 was OR=1.55. Statistical power was subsequently reassessed using OFDs summaries in the first 100 participants enrolled in ACTIV 4 Host Tissue, which demonstrated a more severe distribution relative to PassItOn participants (23.6% vs 17.6% mortality). The estimated MDE85 was OR=1.65 at the time of sample size reassessment. However, additional information from blinded summaries of the first 200 enrolled participants are consistent with the distribution of OFDs observed in PassItOn (18.6% vs 17.6% mortality). After discussion of these findings among the blinded study investigators and study sponsor, it was determined that statistical power was sufficient and no sample size adjustment was warranted.

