Denote a sample of covariate vectors x_1, \dots, x_N and outcomes g_1, \dots, g_N , and corresponding outcome vectors y_1, \dots, y_N , where $y_i = [y_{i1}, \dots, y_{ip}]$. Using this representation, partially observed outcomes are encoded by assigning a value 1 to each element of y_i that the outcome g_i might have taken if fully observed. For example, if g_i might have taken values 1 or 2, but other values were not possible, then y_i would be coded $y_i = [1, 1, 0, \dots, 0]$. Further denote the collection of model parameters $\theta = [\alpha_1, \dots, \alpha_{p-1}, \beta]$. Using this notation, the observed data likelihood is as follows:

$$L(\theta|y_1 \dots y_N, x_1 \dots x_N) = \prod_{i=1}^N L_i(\theta|y_i, x_i) = \prod_{i=1}^N \sum_{j=1}^p I(y_{ij} = 1) \Pr(Y_j = 1|X = x_i), \quad (4)$$

where $I(\cdot)$ is the indicator function that takes a value 1 when its argument is true, and 0 otherwise.

In a Bayesian analysis, the posterior density function is proportional to the likelihood function multiplied by the prior density function as follows:

$$P(\theta|y_1 \dots y_N, x_1 \dots x_N) \propto L(\theta|y_1 \dots y_N, x_1 \dots x_N)P(\theta) \quad (5)$$

A flat prior distribution, where $P(\theta) \propto 1$, is used for all model parameters. Thus, the posterior density is proportional to the likelihood function.

Each supplemental estimand is a treatment difference in one of the following summaries of the adjusted outcome distribution: mean, median, proportion experiencing mortality by day 28, and proportion receiving oxygen every day until day 28. Supplemental estimands are computed using the probabilities expressed in equations (1) and (2) above, adjusted to the modal value for each covariate: age group 31-64, WHO COVID-19 Score value 4 (hospitalized receiving oxygen via nasal cannula), and male sex. The adjusted means are computed as the linear combination of all possible outcome values and their associated adjusted probabilities. The adjusted medians are computed as the smallest value of g such that the $\Pr(G \geq g|X) \geq 0.5$. The adjusted proportions of participants experiencing mortality by day 28 or oxygen requirement every day until day 28 are computed as $\Pr(G = -1|X)$ and $\Pr(G = 0|X)$, respectively.

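### The primary model omits eligibility group and bands age, and the change-score models omit the baseline value: a small forgone gain in precision, not a validity problem

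*SAP*

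**What the plan says.** In SAP 2.3 the permuted block method "with stratification by study site and study arm eligibility is used to generate treatment assignments". SAP 6 then fits the primary model "adjusting for the active drug vs placebo indicator variable, age group (18-30, 31-65, >65 years), sex at birth" and WHO score at baseline in three groups. Protocol 8.6.1 lists the same terms: "age group (18-30, 31-65, >65 years), sex at birth, baseline WHO COVID" score. None of the sensitivity or supplementary analyses in SAP 6.5 adds a stratification factor to the model.

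Eligibility group is defined by which arms a patient could have been assigned to. SAP 2.2: "A participant is considered eligible for a study arm if assignment to that arm was a possible outcome of randomization". Protocol 6.7: "Participants are not eligible for arms that have not begun or have ceased enrollment". SAP 2.2 also treats a patient who declines an arm as ineligible for it.

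The simulation behind the 0.976 threshold and the power table draws age group, sex and WHO score from the observed values, and "their effects on the primary outcome were simulated to match the estimated effects of age group, sex, and WHO score on the primary outcome" (SAP 6.6).

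SAP 6 and Protocol 8.6.1 print the middle age band as 31-65. SAP 11.1 has the supplementary estimands "adjusted to the modal value for each covariate: age group 31-64, WHO COVID-19 Score value 4".

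SAP 7.1.3 analyzes the change outcomes of SAP 3.4 (troponin, NT-proBNP, RAAS markers, creatinine, eGFR) by linear regression on age group, sex and WHO score. It lists no baseline value of the outcome.

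**The concern.** It is usual to carry randomization strata into the analysis model and to use a measured prognostic covariate in full. Age is source-verified and not expected to be missing (SAP 6.2), yet one band covers 35 years and the top band is open-ended.

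Within one arm's comparison everyone is eligible for that arm, so eligibility group records which other arms were open, whether the patient met their criteria, and whether the patient declined them. It could be prognostic: if fostamatinib was open beside another arm, its exclusions on liver tests, blood pressure, neutrophils and strong CYP3A inhibitors (Protocol 22.6) would split the other arm's comparison by health status. If no other arm was open, the group is constant and this part falls away.

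In a proportional odds model, leaving out a prognostic covariate pulls the log odds ratio toward zero; adding it does not shrink the standard error. At stake are slight attenuation and a little power. For the change outcomes, which are exploratory and untested (SAP 5), only the width of credible intervals is at stake.

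**Working it through.** **Inputs.** From SAP 6.3 and 6.6: N = 600, odds ratio 1.65, power 0.856, threshold 0.976 (critical z 1.977), 12% partially observed outcomes, harm looks at 33% and 67%, and the OFD table. Not given, so assumed: an age slope of 0 to 0.05 log odds per year (age mean 57, SD 15), an eligibility-group effect of 0 to 0.8 log odds, WHO and sex effects, and the OFD proportions that the table does not print.

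**1. The printed power.** Whitehead's formula: power = Φ(log OR × √I − 1.977), with I = N/12 × (1 − Σp̄³) and p̄ the mean of the placebo and OR 1.65 columns.
- Death: (0.235 + 0.158)/2 = 0.1965. Zero days: (0.296 + 0.251)/2 = 0.2735. 27 days: (0.050 + 0.081)/2 = 0.0655. The cubes are 0.0076, 0.0205 and 0.0003, and the rest are negligible, so 1 − Σp̄³ ≈ 0.972.
- N = 600: I = 48.6; 0.5008 × 6.97 − 1.977 = 1.51; power 0.935.
- N = 528 (12% lost outright): I = 42.8; 0.5008 × 6.54 − 1.977 = 1.30; power 0.903.

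Simulating the SAP's own fit, with its rule for partial outcomes, gave 0.907 with weak covariate effects, 0.892-0.900 with moderate and 0.874 with very strong ones. The 0.856 is not reproduced. It is not shown to be wrong either, because the covariate effects and the full OFD distribution are not published. The gains below compare models on the same simulated data.

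**2. Gain of continuous age plus eligibility group over the planned model, OR 1.65.**
- Run A: 5,000 replicates per scenario, 30 unequal sites, four groups (45/35/15/5%), blocks within site and group. The gain is the direct difference in power (paired Monte Carlo SE 0.1-0.3 points).
- Run B: 2,500 replicates per scenario, two groups (30% in one). The gain is anchored at the printed power: Φ[(1.063 + 1.977) × R − 1.977] − 0.856, with R the ratio of mean z statistics.

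| Age slope per year | Group effect | Run | Gain, points |
|---|---|---|---|
| 0 | 0 | A | -0.3 |
| 0 | 0 | B | 0.05 |
| up to 0.02 | up to 0.3 | A | 0.3-0.4 |
| 0.02 | 0.3 | B | 0.7 |
| 0.04 | 0 | A | 1.2 |
| 0.04 | 0.3 | B | 1.6 |
| 0-0.02 | 0.67 | A | 0.4-0.9 |
| 0 | 0.8 | B | 1.8 |
| 0.04 | 0.67 | A | 2.0 |
| 0.03 | 0.8 | B | 2.4 |
| 0.05 | 0.5 | B | 2.6 |

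Splitting run B at slope 0.04 and group effect 0.3: eligibility group alone adds 0.32 points, continuous age alone 1.29, both 1.59. At group effects of 0.2-0.3, eligibility group alone adds 0.2-0.3 points.

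The mechanism shows in run A. The mean log odds ratio, planned against fuller model, is 0.498 against 0.499 with no effects and 0.477 against 0.496 at 0.67 and 0.04. The fuller model's standard error is 0.1%-0.5% larger.

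For scale, one point above 0.856 is worth ((1.977 + 1.108)/(1.977 + 1.063))² ≈ 1.03, or about 18 of 600 patients.

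**3. Type I error.** Four null scenarios, 10,000 replicates each, harm looks at 200 and 400 patients. Planned model: (2.60 + 2.40 + 2.06 + 2.49)/4 = 2.39%. Fuller model: (2.48 + 2.53 + 2.09 + 2.63)/4 = 2.43%. The SE is 0.08%.

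**4. Site.** Flat-prior site fixed effects rejected 3.1%, 2.9% and 2.5% under the null with 30, 40 and 60 sites, against 2.6%, 2.5% and 2.2% for the planned model on the same data. The paired excess is 0.3-0.6 points (SE 0.1).

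**5. Change scores.** With k = follow-up SD / baseline SD and correlation ρ, adding the baseline value multiplies residual variance by k²(1 − ρ²)/(k² + 1 − 2ρk). At k = 1 this is (1 + ρ)/2: 0.65 at ρ = 0.3 and 0.85 at ρ = 0.7, a cut of 35% to 15%. Interval width falls by 1 − √0.65 = 19% to 1 − √0.85 = 8%. With unequal SDs, the cut is 58% at k = 0.7, ρ = 0.3 (0.446/1.07 = 0.42) and about 0% at k = 1.5, ρ = 0.7 (1.1475/1.15 = 1.00).

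**The case against.** The strongest reply is that no error is shown. The placebo comparator is already eligibility-matched and balanced with active within blocks, and the model already holds WHO score, age group and sex. The attenuation is non-collapsibility: a different conditional odds ratio, not bias. That stands.

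The evidence on eligibility group is also thin. No document gives its prognostic effect or its distribution within any comparison, and the group layouts above are invented. The two runs differ on a strong group effect (0.4-0.9 points at 0.67, 1.8 at 0.8). At modest effects the gain from the group alone is about the size of the 0.3-point loss when the added terms carry no information. That stands too, and it makes age the firmer part.

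The remedy also has costs: a pooling rule, a reference age and a rerun of the threshold simulation. For an arm past its first interim, changing the primary model would be worse than leaving it. The fix allows for this.

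The reply does not remove the point. The data are already collected, null rejection is essentially unchanged, no analysis in SAP 6.5 examines the omission, and the age-band conflict needs correcting in any case. The baseline values are also available: Table 1 of the protocol places baseline blood work before treatment.

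**Conclusion.** The point holds as a minor improvement. Relative to the planned model, a finer one changes power by about -0.3 points with no true effects to about 2 points with strong ones (2.6 at the extreme assumptions). Most of this comes from age unless eligibility group is strongly prognostic. All of it rests on assumed effects, and the eligibility part is nil for a comparison in which only one arm was open.

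Three stronger readings are tempting and are not supported.
- A reader might infer that the printed 0.856 is overstated by up to 2 points. SAP 6.6 simulated it with age group and the planned analysis, so banding is already in it. The gain is forgone, not lost.
- A reader might infer that omitting a stratum invalidates the test. The 1:1 balance within blocks and the null rates of 2.39% and 2.43% say otherwise.
- A reader might take the change in mortality as evidence of a large group effect. Mortality was 23.6% in the first 100, while the first 200 "are consistent with the distribution of OFDs observed in PassItOn (18.6% vs 17.6% mortality"). If the 100 lie within the 200, the second 100 had 2 × 18.6 − 23.6 = 13.6%, a log-odds gap of 0.67 (95% CI -0.06 to 1.41). That is a calendar-time difference, unadjusted and compatible with zero, and nothing links it to arms opening or closing. It should not be used to size the effect.

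For the change scores, the variance cut of 35% to 15% assumes equal SDs.

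**What to change.** 1. **SAP 7.1.3.** Add the baseline value of each change outcome as a covariate. RAAS markers stay subject to the separate sub-study SAP (SAP 1.1).
2. **SAP 6 and Protocol 8.6.1, arms before their first interim** (the amendment limit in Protocol 8.1). Enter age as linear plus quadratic. Add eligibility group as a fixed effect where it varies within the comparison, with a fixed pooling rule: for example, a group with under 5% of the comparison's patients joins the largest. Both are extra columns in the covariate matrix of SAP 11.3 and keep the flat prior. In SAP 6.4 and 11.1, state a reference age for the supplementary estimands, such as the blinded pooled median. Rerun the null simulation to confirm 0.976.
3. **Arms past their first interim.** Keep the planned model and pre-specify the fuller one as a sensitivity analysis before unblinding.
4. **If bands are kept**, reconcile 31-65 with 31-64, which decides where a 65-year-old falls.
5. **Site** belongs only in a sensitivity analysis in SAP 6.5, with a random or penalized intercept or pooled regions.

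Cost: a small SAP amendment and one simulation rerun, with no new data. The odds ratio becomes conditional on slightly more covariates. If the added terms carry no information, up to about 0.3 points of power are lost.
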